7.1 Study Design

This is a descriptive cohort study using secondary data sources (electronic medical records) from eight databases in seven European countries reflecting either hospital or ambulatory care setting. The study population will be comprised of a cohort of diagCOVID-19 or labCOVID-19 patients in the database within the study time period.

Patients may be either diagnosed and followed-up in an outpatient or in an inpatient setting (according to the database) and they might be new users or prevalent users of systemic glucocorticoids. Based on these 2 characteristics, four mutually exclusive cohorts will be created overall. Not all cohorts can be constructed in each database. They will be used differently depending the objective as mentioned in the analysis section. An overview of the study design is provided in Figure 1 below.

Patients will be followed during the study period from COVID-19 diagnosis date to assess the utilization of systemic glucocorticoids specifically indicated for the treatment of COVID-19 and from treatment index date for the occurrence of outcomes of interest.

[figure not shown]

Figure 1 Study design

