7.2.2 Patient Selection

7.2.2.1 Inclusion Criteria

Four cohorts will be created based on healthcare setting and type of steroid use. Their eligibility criteria being described below (using Covid-19 catch-all definition Section 7.3.1):

Ambulatory prevalent user

- Have at least 365 days of continuous observation time prior to cohort entry
- Have a glucocorticoid (oral or parenteral) exposure in the 120 days prior to diagnosis date (unrelated to COVID-19 diagnosis)
- Have a positive PCR test for SARS-CoV-2 (labCOVID-19) or a confirmed COVID-19 diagnosis (diagCOVID-19)
- Have no hospitalizations in the 30 days prior to or on index

Ambulatory naive user

- Have at least 365 days of continuous observation time prior to cohort entry
- Have no glucocorticoid (oral or parenteral) exposure in the 120 days prior to index (unrelated to COVID-19 diagnosis)
- Have a positive PCR test for SARS-CoV-2 (labCOVID-19) or a confirmed COVID-19 diagnosis (diagCOVID-19)
- Have no hospitalizations in the 30 days prior to or on index

Hospitalized prevalent user

- Have a glucocorticoid (oral or parenteral) exposure in the 120 days prior to index (unrelated to COVID-19 diagnosis)
- Have a positive PCR test for SARS-CoV-2 (labCOVID-19) or a confirmed COVID-19 diagnosis (diagCOVID-19) (index date)
- Are hospitalized 30 days prior or after diagnosis index date
- Have no intensive services in the 30 days prior to or on index

Hospitalized naïve user

- Have no prior exposures to glucocorticoids in the 120 days prior to index
- Have a positive PCR test for SARS-CoV-2 (labCOVID-19) or a confirmed COVID-19 diagnosis (diagCOVID-19)
- Are hospitalized 30 days prior or after diagnosis index date
- Have no intensive services in the 30 days prior to or on index

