7.2.3 Follow-up

Two index date definitions will be applied as appropriate for each objective.

- Diagnosis index date is defined as a positive PCR test for SARS-CoV-2 (labCOVID-19) or a confirmed COVID-19 diagnosis(diagCOVID-19) whichever is the earliest.
- Treatment index date is defined as start of first systemic glucocorticoid treatment episode specifically for the treatment of COVID-19, irrespective of whether the patient is a prevalent or naïve user.

Follow up for all patients will begin from the index date until they experience the outcome of interest (endpoint, depending on the objective) or until cohort exit (date of censoring). The patients will be followed up for maximum 90 days or until censoring occurs, censoring criteria are:

- death
- patient exit (deregister) from a contributing data provider (GP practice)
- end of the database's data collection
- end of study period (latest data cut-off)

The lookback window for evaluating risk factors, medical history is 365 days and will be applied only to outpatient cohorts.

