7.3.4 Disease severity outcomes

In ambulatory care cohorts

- Hospital admission
- Venous thromboembolism (VTE) or pulmonary embolism (PE)
- Disseminated intravascular coagulation (DIC)
- Death of any cause

In hospitalized cohorts

- Intensive services as an outcome in inpatient cohorts (including mechanical ventilation and Extracorporeal membrane oxygenation (ECMO))
- Discharge from hospital
- Death of any cause
- Venous thromboembolism (VTE) or pulmonary embolism (PE)
- Disseminated intravascular coagulation (DIC)

They will all be treated as time to event outcomes, see section 7.7 for details.

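### Hospital-cohort entry can depend on an admission up to 30 days after diagnosis while the clock starts at diagnosis, and a stay that ended before diagnosis also qualifies

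*Protocol*

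**What the plan says.** All references are to the Protocol.

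- **Hospital entry (7.2.2.1).** Both hospitalised cohorts take patients who "Are hospitalized 30 days prior or after diagnosis index date". They must also have had no intensive services in the 30 days up to and including index.
- **Ambulatory entry (7.2.2.1).** Patients must "Have no hospitalizations in the 30 days prior to or on index". Admission after index is allowed. Sections 7.2 and 7.3.4 make it an outcome of the ambulatory cohorts.
- **Clock (7.2.3).** "Diagnosis index date is defined as a positive PCR test for SARS-CoV-2 (labCOVID-19) or a confirmed COVID-19 diagnosis", whichever comes first. "Follow up for all patients will begin from the index date until they experience the outcome of interest" or are censored, for at most 90 days. No delayed-entry rule is given.
- **Primary objective (6.2, 7.7.2).** Utilisation is described by setting. The Kaplan-Meier analysis of time to glucocorticoid initiation runs from diagnosis.
- **Outcomes (7.1, 7.2.3).** Patients are followed "from treatment index date for the occurrence of outcomes of interest". "Treatment index date is defined as start of first systemic glucocorticoid treatment episode specifically for the treatment of COVID-19".
- **Exclusivity (7.1).** "Based on these 2 characteristics, four mutually exclusive cohorts will be created overall". Section 7.2 assigns setting by type of data source.
- **Data (7.4, 7.5).** HM Hospitales covers in-patient care and is the only database observing hospitalised patients, around 2,000 of them. Only SIDIAP links primary and secondary care.

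**The concern.** Setting is the main stratifier of the primary objective, and for some patients it is decided by what happens after time zero. Take a patient diagnosed on day 0 and admitted on day 12. This patient is in the hospital cohort from day 0, although entry required reaching admission alive, and no in-patient drug could be recorded in those 12 days. A similar patient who died or recovered without admission can never enter. The hospital time-to-initiation curve then mixes waiting for admission with waiting for treatment once in hospital, and the baseline table describes some hospital patients at a date when they were at home.

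Two further faults sit in the same rule. Before diagnosis, a patient discharged on day -20 and diagnosed at home qualifies as hospitalised, is barred from the ambulatory cohorts, and can no longer have discharge from that stay as an outcome. And one admission after diagnosis is an entry criterion for one cohort and an outcome for another, although the four cohorts are declared mutually exclusive.

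**Working it through.** The plan gives no figure to reproduce. The check lists the eligibility rules by day and then counts days.

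**1. Which admission days meet which setting rule.** Let *a* be the admission day relative to diagnosis (day 0), with a single admission, all other criteria met and day 0 counted as inside the hospital window.
- Hospital rule: -30 ≤ *a* ≤ +30, which is 30 + 1 + 30 = 61 days.
- Ambulatory rule: *a* not in -30 to 0.
- Both rules: +1 ≤ *a* ≤ +30, which is 30 of the 61 days. No admission day fails both.

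**2. Pre-admission time in the hospital risk set.** For *a* > 0 it lasts *a* days. Section 7.3.2.1 attributes a glucocorticoid to COVID-19 only if started from day -2 to day +30, a window of 33 days. The part of that window spent after admission is at most 30 - *a* + 1 days.

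| Admission day | Share of first 30 days | Share of 90 days | Attribution days left from admission |
|---|---|---|---|
| 5 | 5/30 = 17% | 5/90 = 6% | 26 of 33 |
| 10 | 10/30 = 33% | 10/90 = 11% | 21 of 33 |
| 30 | 30/30 = 100% | 30/90 = 33% | 1 of 33 |

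**3. Which analyses use the diagnosis clock.**
- Affected: time to initiation, utilisation within 90 days of diagnosis, and characteristics at diagnosis.
- Largely unaffected: outcome rates in glucocorticoid-treated groups. Their clock starts at the first glucocorticoid, and an in-patient start recorded in HM Hospitales normally falls at or after admission.
- Unclear: the groups with other treatments only or no specific treatment. The treatment index date is defined only by a glucocorticoid start, and Section 7.7.4 refers just to the relevant index date.

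**4. Illustration for a rate clocked from diagnosis.** This matters only if the unclear groups fall back to diagnosis. The inputs are assumptions, not Protocol figures: hazard *h* = 0.01 per day after admission, a 30-day window, and a fraction *f* admitted *d* days after diagnosis.
- Admitted by day 0: events *E₀* = 1 - exp(-30*h*) = 0.259; person-days *E₀*/*h* = 25.9.
- Admitted on day *d*: events *E₁* = 1 - exp(-(30 - *d*)*h*); person-days *d* + *E₁*/*h*.
- Rate = 1,000 × [(1 - *f*)*E₀* + *f* *E₁*] / [(1 - *f*)*E₀*/*h* + *f*(*d* + *E₁*/*h*)].
- *f* = 0.1, *d* = 3: 9.88 per 1,000 patient-days against a true 10, about 1% low.
- *f* = 0.5, *d* = 14: 7.44, about 26% low.

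**5. After the change.** With hospital time starting at the later of diagnosis and admission, the pre-admission interval in the hospital risk set is 0 days, against up to 30 as written.

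**The case against.** **The lag may be close to zero.** If HM Hospitales sees only in-patient care, a diagnosis made before admission would normally be invisible there too. Section 7.9.1 says PCR results are currently available only in SIDIAP, so the HM index probably rests on an in-patient record. The same reasoning makes a patient diagnosed at home after discharge hard to find in that source. This stands as a limit on size. It does not rescue the rule: Section 3.0 records that admission after diagnosis was added on purpose, and where it applies, it conditions on the future.

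**Setting is fixed by database.** Section 7.2 assigns it by data source, and Section 7.5 counts one source observing hospitalised patients. A reader might infer from the bullets that every patient admitted on days +1 to +30 is counted twice. The Protocol does not support that: overlap needs both cohorts in one database, linked SIDIAP being the possible case. Section 7.9.2 says some primary care databases capture hospitalisation, but not that they build hospital cohorts. What remains is that the bullets alone do not deliver the exclusivity claimed in Section 7.1.

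**Time from diagnosis is the declared measure.** A reader might say time to initiation is overstated by exactly the admission lag. It is not. Twelve days from diagnosis to first dose is the right value of the measure in Section 6.2. The fault is to present those days as time at risk in hospital.

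**Figure 1 is not visible in the text reviewed** and may clarify the timing.

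**Conclusion.** The point holds for the hospital-cohort entry rule and the diagnosis-clocked descriptions built on it: the primary objective and the baseline tables. Admission on days +1 to +30 is a future condition for entry, up to 30 days of admission-guaranteed and unobservable time enters the hospital risk set, and a completed prior stay qualifies. The criteria and the exclusivity statement need reconciling.

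The size cannot be derived. It depends on how often, and by how long, diagnosis precedes admission in HM Hospitales, which the Protocol does not give; the effect may be small. A reader might also infer that hospital outcome rates in general are diluted. That does not follow for glucocorticoid-treated groups, and the 1% to 26% illustration rests wholly on assumed inputs and a clock that the Protocol does not clearly assign to anyone.

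This should be fixed, but it does not undermine the study as a whole. Section 7.2.1 says results will not be refreshed after extraction, so it is best settled before then.

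**What to change.** Amend Sections 7.2.2 and 7.2.3:

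1. Keep the 30-day window after diagnosis, but start hospital-cohort entry and risk time at the later of diagnosis and admission (delayed entry), and describe baseline at that date.
2. For a stay that began before diagnosis, require it to be ongoing at diagnosis.
3. Still report time from diagnosis to initiation, with days from diagnosis to admission as a descriptor.
4. State that admission of an ambulatory patient is an ambulatory outcome, and that such a patient can contribute hospital time only from admission.

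**Cost.** Wording, plus a change to cohort code run on secondary data. Two clocks must be reported, and a few patients with completed stays leave the hospital cohort. The intensive-services criterion must be reconciled with the new entry date: if its check moves there, patients ventilated on the day of admission after an earlier diagnosis would be excluded, whereas now they can pass.

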6.3 Secondary Objectives

1. To describe **at COVID-19 diagnosis date and at treatment index date** the demographic, health and clinical patient characteristics. The following variables will be described:
 - demographics
 - comorbidities (number and type)
 - symptoms (number and type) preceding and/or on the date of diagnosis the diagnosis if captured time from onset of COVID-19 illness symptoms to confirmed diagnosis date.

Some of these characteristics will be stratified by setting, glucocorticoid exposure type (naive, prevalent) and subgroups of special interest. (e.g., chronic cardiac and pulmonary disease, diabetes, renal insufficiency, see Section 7.2.4 Subgroups).

2. To quantify the crude and adjusted (selected confounders tbc) incidence rates and time to onset of adverse events of interest (e.g., infections, hyperglycaemia, hypertension, GI bleeding, composite of cardiovascular events) within **30 and 90 days post treatment index date**, in **various treatment groups**, stratified by setting, glucocorticoid exposure type (naive, prevalent) and subgroups of special interest.

3. To quantify the crude and adjusted incidence rates of mortality and other disease outcomes within **30 and 90 days post treatment index date**, in **various treatment groups**, stratified by setting, glucocorticoid exposure type (naive, prevalent) and subgroups of special interest.

4. To explore the performance of **different coding definitions** for COVID-19 and how they influence the size of the cohort

Out of scope:

To assess comparative effectiveness and safety between individual treatments administered for COVID-19 infection or between treated and untreated patients.

To validate definition for COVID-19 using clinical adjudication of individual patient medical records sampled from the study population

[figure not shown]
Section 7.0 Research Methods

[figure not shown]
[figure not shown]

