7.3.2.1 Glucocorticoids

Glucocorticoids used in COVID-19 indication

The primary treatment group of interest is based on exposure to systemic glucocorticoids. The following drugs will be considered as being used for COVID-19 diagnosis:

- Dexamethasone (H02AB02)
- Prednisone (H02AB07)
- Prednisolone (H02AB06)
- Methylprednisolone (H02AB04)
- Hydrocortisone (H02AB09)

Only glucocorticoids which were investigated in clinical trials (13,21) or are recommended by clinical guidelines are included (22–24) to avoid misclassification of steroids used for other conditions. As indication is not captured in the available databases, a glucocorticoid treatment will be considered to have been initiated for COVID-19 treatment if:

For incident users

- The glucocorticoid treatment was initiated between 2 before and 30 days after COVID-19 diagnosis date (21)
- It is one of the five glucocorticoids recommended for COVID-19 as above

For prevalent users

- The glucocorticoid treatment was initiated between 2 before and 30 days after COVID-19 diagnosis date
- It is one of the five glucocorticoids recommended for COVID-19 as above
- The glucocorticoid started after COVID-19 diagnosis differs from the chronically used glucocorticoids OR there is a change in dose or schedule of administration compared to the prevalent use, occurred after COVID-19 diagnosis.

Glucocorticoids for pre-existing conditions

For the prevalent users, any steroid in the ATC class H02 glucocorticoids for systemic use will be considered. A patient is defined as a systemic glucocorticoids prevalent user if it has at least one prior exposure to systemic² glucocorticoids in the 120 days prior to diagnosis index date.

For the description of prevalent users of glucocorticoids, categories of use will be created based on proportion of days covered (PDC) during the lookback period. PDC is calculated as the number of days in period covered by prescriptions divided by number of days in the period.

- PDC > 85% as heavy user
- PDC 50-85% as moderate user
- less than 50% PDC as light user

Another categorization of prevalent glucocorticoids user will be based on how recently in the past the last prescription was observed:

- current use (concomitant on date of COVID-19 diagnosis)
- recent use (between 15-30 days before date of COVID-19 diagnosis)
- remote use (use ended more than 30 days before date of COVID-19 diagnosis)

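### Intensive services are screened at COVID-19 diagnosis but counted as an outcome from glucocorticoid start up to 30 days later, so patients ventilated in between enter follow-up already having had the event

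*Protocol*

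**What the plan says.** **Screen.** Each hospitalized cohort in 7.2.2.1 must "Have no intensive services in the 30 days prior to or on index". Each ambulatory cohort must "Have no hospitalizations in the 30 days prior to or on index".

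**Which index.** In the hospitalized prevalent-user list, the case criterion ends "or a confirmed COVID-19 diagnosis (diagCOVID-19) (index date"), so index is the diagnosis or positive PCR. Section 7.3.2.1 restates the parallel prior-exposure criterion as exposure "in the 120 days prior to diagnosis index date". Section 7.2.3, however, says "Two index date definitions will be applied as appropriate for each objective", and the two screening bullets do not say which date they use.

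**Outcome clock.** Objective 3 in 6.3 is "To quantify the crude and adjusted incidence rates of mortality and other disease outcomes within" 30 and 90 days of the treatment index date. Section 7.2.3 defines that date as the start of the first glucocorticoid episode for COVID-19. Under 7.3.2.1 the episode qualifies if "The glucocorticoid treatment was initiated between 2 before and 30 days after COVID-19 diagnosis date".

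**Outcome.** For hospitalized cohorts, 7.3.4 lists "Intensive services as an outcome in inpatient cohorts (including mechanical ventilation and Extracorporeal membrane oxygenation (ECMO"). For ambulatory cohorts it lists hospital admission.

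**Counting rule.** Section 7.7.4 refers to incident events and to a population at risk. Its numerator, though, is the number of patients with the outcome recorded in the time frame after that type of person-time began. It has no rule for patients who had the event before the clock started.

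**The concern.** The protocol has a washout for intensive services, but it ends at one time zero while the outcome clock starts at another. Section 7.9.1 says glucocorticoids are indicated in severe cases only, so ventilation followed by a glucocorticoid is a foreseeable sequence in the hospital cohorts. For such a patient, an event that preceded treatment, and may have prompted it, could be reported as an outcome following treatment. Alternatively, the patient contributes time in which a first event can no longer occur. Which of these happens depends on a choice the protocol does not state, so a reader of the final report could not tell the direction of the error.

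**Working it through.** **Dates, with diagnosis as day 0**

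| Item | Window | Source |
|---|---|---|
| Intensive-services screen | day −30 to day 0 | 7.2.2.1 |
| Glucocorticoid start (treatment index) | day −2 to day +30 | 7.3.2.1, 7.2.3 |
| Outcome follow-up | treatment index to 30 and 90 days later | 6.3 |
| Not covered by the screen | after day 0 up to treatment index, at most 30 days | difference |

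Take a patient ventilated on day 3 who starts a glucocorticoid on day 5. The patient passes the screen and enters follow-up on day 5 already ventilated.

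**Where the patient is placed.** Section 7.3.2.3 assigns exposure groups at treatment index and has a group for glucocorticoids with other treatment, including respiratory support. Section 7.3.5 counts invasive ventilation and ECMO on or after diagnosis as respiratory support. Anyone ventilated by day 0 has been excluded, so a patient in this group who is already ventilated at a later treatment start was first ventilated in the unscreened interval. One ventilation episode can then both assign the group and be scored as that group's outcome.

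**How the patient is scored.** The intensive-services list in Appendix 1 (4.3) includes concepts that describe a continuing state: ventilator dependence, an endotracheal tube in place, ventilator care, and weaning. Such records after day 5 satisfy the 7.7.4 numerator as written.

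**Size.** The protocol gives no figure to reproduce. Let f be the assumed share of the reported glucocorticoid group already ventilated at treatment index, and r the assumed true 30-day risk in the rest.

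- Continuing records counted: f + (1 − f)r
- Not counted, denominator unchanged: (1 − f)r

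| r | f | Counted | Not counted |
|---|---|---|---|
| 20% | 10% | 0.10 + 0.90 × 0.20 = 28% | 0.90 × 0.20 = 18% |
| 20% | 30% | 0.30 + 0.70 × 0.20 = 44% | 0.70 × 0.20 = 14% |
| 10% | 10% | 0.10 + 0.90 × 0.10 = 19% | 0.90 × 0.10 = 9% |
| 10% | 30% | 0.30 + 0.70 × 0.10 = 37% | 0.70 × 0.10 = 7% |

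**On the rate scale,** assume a constant hazard over 30 days and no other censoring. With r = 20% the hazard is −ln(0.80)/30 = 7.44 per 1,000 patient-days, and mean time at risk is 0.20/0.00744 = 26.9 days. With f = 10%:

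- Not counted: 0.18/(0.90 × 26.9 + 0.10 × 30) = 6.6 per 1,000 patient-days
- Counted, with the record placed on day 1: 0.28/(0.90 × 26.9 + 0.10 × 1) = 11.5 per 1,000 patient-days

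Removing the already-ventilated patients from this outcome's risk set returns r in every row.

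**The case against.** The strongest reply is that 7.7.4 already speaks of incident events and a population at risk. On that view a ventilated patient is plainly not at risk of starting ventilation, and the filter is SAP detail in a document not at hand. The principle is indeed there. But the numerator sentence in the same section works against it, because it looks only for a record after the clock starts, and the code list contains continuing states. The protocol therefore states a rule that gives the wrong count, which is more than leaving a detail open.

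Second, index is unlabelled in the screening bullets and two index dates exist, so re-application at treatment start may have been intended. That is possible, but the surrounding text points to diagnosis and no section says otherwise.

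Third, the reach is limited, and this stands. Section 7.5 says only one database observes hospitalized patients, around 2,000 of them. Already-ventilated patients should fall mainly in the combined-treatment group and leave the glucocorticoid-only group largely untouched. Section 7.9.1 also rules out comparative analysis and warns about severity when rates are interpreted, which limits causal misreading without curing the count.

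A reader might infer that the ambulatory admission outcome is affected in the same way. It is not, because admission can recur: a patient admitted, discharged and then given a glucocorticoid is properly at risk of a new admission. Section 7.4 adds that only SIDIAP links primary and secondary care, so many earlier admissions cannot be seen at all.

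**Conclusion.** The mismatch is real for intensive services in the hospitalized cohorts, within the glucocorticoid-treated groups and mainly the combined-treatment group. It does not touch the primary objective, and the other outcomes are not affected by this route.

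The direction is not fixed. Counting continuing records inflates the risk, and not counting them dilutes it. With 10% to 30% already ventilated and a true risk of 20%, the reported risk is 28% to 44% or 18% to 14%. Both inputs are assumptions. A reader might take these figures as estimates for the hospital database, or conclude that ventilation before treatment is common there. The protocol supports the path as foreseeable but says nothing about how frequent it is.

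Nor can the point be extended to all four treatment groups. The treatment index date is defined only by glucocorticoid start, so the two groups without a glucocorticoid have no such date.

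**What to change.** 1. In 7.2.2.1, state that index means the diagnosis index date.
2. In 7.7.4, for the intensive-services outcome only, exclude from the at-risk set glucocorticoid-treated patients with any intensive-services record from diagnosis through treatment index, both days included.
3. Keep these patients for death, VTE/PE, DIC and the adverse events, and report the number removed in each of the two glucocorticoid groups.
4. For hospital admission in the ambulatory cohorts, exclude only patients still in hospital at treatment index, where admission is recorded. Patients already discharged stay at risk of a new admission.
5. Note that the filter cannot be applied to the two groups without glucocorticoids until a treatment index date is set for them.

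The cost is a few sentences and one at-risk filter per outcome, with no new data. Somewhat fewer patients will contribute to these two outcomes. With one hospital source of about 2,000 patients, the number lost should be checked before the rates are reported.
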